| Hematologic Improvement (HI)   | 
 
HI indices as defined in the IWG 2006 criteria, without requirement of EHR documentation
 
  |
| Relapse After CR or PR   | 
At least 1 of the following:
 
 
Return to pretreatment BM blast percentage
 
Decrement of <math>\geq 50\%</math> from maximum remission/response levels in granulocytes or platelets
 
Reduction in Hb concentration by <math>\geq 1.5</math> g/dL
 
Transfusion dependence
 
  |
| Stable disease (SD) or Real-World Stable Disease (rw-SD) or Indeterminate Response | 
 
EHR documentation of disease as “stable” and
 
IWG 2006 indices not meeting the threshold for PD (see below) for a minimum of 8 weeks
 
   |
| Progressive Disease (PD)   | 
 
EHR documentation of “progressed disease” or “worsening of disease” or similar terms or
 
 
For patients with:
 
 
Less than 5% blasts: <math>\geq 50\%</math> increase in blasts to <math>> 5\%</math> blasts
 
5%-10% blasts: <math>\geq 50\%</math> increase in blasts to <math>> 10\%</math> blasts
 
10%-20% blasts: <math>\geq 50\%</math> increase in blasts to <math>> 20\%</math> blasts
 
20%-30% blasts: <math>\geq 50\%</math> increase in blasts to <math>> 30\%</math> blasts
 
 
Any of the following:
 
 
At least 50% decrement from maximum remission/response in granulocytes or platelets
 
Reduction in Hb by <math>\geq 2</math> g/dL
 
Transfusion dependence
 
 |

BM bone marrow; CR complete remission; EHR electronic health record; Hb hemoglobin; HI hematologic improvement; IWG International Working Group; mCR marrow complete remission; MDS myelodysplastic syndrome; PD progressive disease; PR partial remission; rw CR real world CR; rw PR real world partial remission; rw SD real world stable disease  
 Cytogenetic responses are not defined for simplicity.

All responses meeting the CR, rw CR, PR, and rw PR will be subject to adjudication by an independent assessor who will be a board certified hematologist.

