### 8.1.2. Secondary Endpoints

**Real -World Complete Remission (rw-CR) Rate** is defined as the proportion of patients who achieve a CR as documented within their EHRs with or without confirmation of corresponding BM and peripheral blood parameters as defined per IWG 2006 MDS response criteria, during the treatment period with AZA or prior to the initiation of next MDS treatment.

**Objective Response Rate (ORR)** is defined as the proportion of patients who achieve a CR, or PR as documented within their EHRs with confirmation of corresponding BM and peripheral blood parameters as defined per IWG 2006 MDS response criteria, or achieve an mCR or HI, during the treatment period with AZA or prior to the initiation of next MDS treatment.

**Real -World Objective Response Rate (rw-ORR)** is defined as the proportion of patients who achieve a CR, or PR, as documented within their EHRs with or without confirmation of corresponding BM and peripheral blood parameters as defined per IWG 2006 MDS response criteria, or achieve an mCR or HI, during the treatment period with AZA or prior to the initiation of next MDS treatment.

**Duration of CR (DCR)** is defined as the interval from the first EHR documentation of a CR with confirmation of corresponding BM and peripheral blood parameters as defined per IWG 2006 MDS response criteria to the earlier of the first documentation of relapse, disease progression, or death from any cause.

**rw-DCR** is defined as the interval from the first EHR documentation of a CR with or without confirmation of corresponding BM and peripheral blood parameters as defined per IWG 2006 MDS response criteria to the earlier of the first documentation of relapse, disease progression, or death from any cause.

**Duration of Response (DOR)** is defined as the interval from when the criteria are first met for OR to the earlier of the first documentation of relapse, disease progression, or death from any cause.

**rw-DOR** is defined as the interval from when the criteria for rw-OR are first met to the earlier of the first documentation of relapse, disease progression, or death from any cause.

**Progression -Free Survival** is defined as the interval from the date of initiation of AZA to the earlier date of the first documentation of relapse, disease progression or death from any cause.

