**Table 8-2. Definition of Data Collection End Date**

[figure not shown]
| Scenarios |   | Data Collection End Date  |
|-----------|---|---|
| A  | Patient remains on AZA throughout (beyond 01 January 2021)                | 01 January 2021   |
| B  | Patient has progression on AZA and AZA is discontinued                    | 30 days after discontinuation of AZA
(Data relating to survival and next treatment will be collected beyond this date.)                |
| C  | Patient discontinues AZA due to toxicity or investigator/patient decision | 30 days after discontinuation
(Data relating to date of progression, survival, and next treatment will be collected beyond this date.) |
| D  | Patient dies while receiving AZA  | Date of death   |
| E  | Patient is lost to follow-up  | Date of last available data   |

AZA azacitidine

In all scenarios, data collection starts on the date of AZA initiation.

The different scenarios for patient inclusion are shown in [Figure 8-1](#) below.

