| BM Blasts % at MDS Diagnosis  | 1&2   | Unstructured | X   |              |         |           |                       |
| BM Blasts % at AZA Initiation   | 1&2   | Unstructured | X   |              |         |           |                       |
| BM Blasts During Treatment  | 1&2   | Unstructured |   | X            | X       | X         | X                     |
| Peripheral Blasts During Treatment  | 1&2   | Unstructured |   | X            | X       | X         | X                     |

| Data to be Provided if Available or Applicable  | Stage | Source                    | Baseline (At AZA Initiation or Earlier as Applicable) | Study Period |         |           | Post-treatment Period |
|---|-------|---------------------------|---|--------------|---------|-----------|-----------------------|
|   |       |                           |   | Visit 1      | Visit 2 | Visit (n) | Post-treatment        |
| Requirement for Blood Transfusion (record units and frequency)  | 2     | Unstructured              | X   | X            | X       | X         |                       |
| ECOG/Karnofsky Performance Status/  | 1&2   | Structured                | X   | X            | X       | X         |                       |
| Comorbidity b  | 1&2   | Structured                | X   |              |         |           |                       |
| Prior Treatment for MDS Including Supportive Care c  | 1&2   | Structured + Unstructured | X   |              |         |           |                       |
| Information Collected at Baseline and During the Study   |       |                           |   |              |         |           |                       |
| Concomitant Medications   | 1&2   | Structured + Unstructured | X   | X            | X       | X         | X                     |
| Complete Blood Count d   | 1&2   | Structured                | X   | X            | X       | X         | X                     |
| Serum Chemistry e  | 1&2   | Structured f   | X   | X            | X       | X         | X                     |
| Liver Function Tests g   | 2     | Structured                | X   | X            | X       | X         | X                     |
| AZA Treatment-Related Data   |       |                           |   |              |         |           |                       |

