| Dose Changes h   | 2     | Structured + Unstructured | X   | X            | X       | X         |                       |
| Dose Interruptions i   | 2     | Structured + Unstructured | X   | X            | X       | X         |                       |
| Discontinuation h  | 1&2   | Structured + Unstructured | X   | X            | X       | X         |                       |
| Reason for Treatment Discontinuation  | 1&2   | Unstructured              |   |              |         | X         | X                     |
| Data Related to Effectiveness  |       |                           |   |              |         |           |                       |
| Date of Response Assessment (From Progress Notes and/or Attachment for the Bone Marrow Report)                                | 1&2   | Unstructured              | X   | X            | X       | X         |                       |
| Response Category j (From Progress Notes and/or Attachment for the Bone Marrow Report)                             | 1&2   | Unstructured              | X   | X            | X       | X         |                       |
| IWG 2006 Response Assessment, Where Available k (From Progress Notes and/or Attachment for the Bone Marrow Report) | 1&2   | Unstructured              | X   | X            | X       | X         | X                     |
| If Progression, Date of Progression   | 1&2   | Unstructured              |   | X            | X       | X         | X                     |

| Data to be Provided if Available or Applicable                         | Stage | Source                            | Baseline (At AZA Initiation or Earlier as Applicable) | Study Period |         |           | Post-treatment Period |
|--|-------|-----------------------------------|---|--------------|---------|-----------|-----------------------|
|  |       |                                   |   | Visit 1      | Visit 2 | Visit (n) | Post-treatment        |
| Last USON Visit Date   | 2     | Structured + unstructured         |   | X            | X       | X         | X                     |
| Death Date   | 2     | Structured + LADMF + unstructured |   | X            | X       | X         | X                     |
| MDS Treatment After Discontinuation of AZA, if Applicable l | 1&2   | Structured + Unstructured         |   | X            | X       | X         | X                     |

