### 8.7.4. Effectiveness Analyses

For the primary effectiveness analysis, CR rates will be evaluated using the FAS. The point estimate and the corresponding 95% CIs based on the Clopper-Pearson exact method will be provided. The same method will be applied to rw-CR, ORR, and rw-ORR using the FAS.

The time-to-event effectiveness endpoints including PFS, DCR, rw-DCR, DOR, rw-DOR, TTNT, and OS will be analyzed using the Kaplan-Meier method. Kaplan-Meier curves will be provided for the time-to-event endpoints. The endpoints of PFS, TTNT, and OS will use FAS. DCR and rw-DCR will include the FAS patients who achieve a CR or rw-CR, respectively. DOR and rw-DOR will include the FAS patients who achieve an OR or rw-OR, respectively.

CCI

Sensitivity analyses will be performed for the primary and secondary endpoints (except DCR, rw-DCR, DOR, and rw-DOR) using EEAS.

The results of this study will be compared to the ongoing Phase 1b single -arm study of magrolimab + AZA (Study 5F9005) in patients with untreated higher-risk MDS. A detailed statistical analysis for comparison will be described in the statistical analysis plan.

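### Blood transfusions are not scheduled for abstraction after azacitidine stops, although transfusion dependence is a progression and relapse criterion and PFS, DCR and DOR run past that point

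*Protocol*

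**What the plan says.** Table 8-1 (section 8.1.1) lists "Transfusion dependence" among the alternatives that each suffice for progressive disease, and again among those that suffice for relapse after CR or PR. Table 13-1 (Appendix 2) repeats it under both.

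Section 8.1.2 says that PFS "is defined as the interval from the date of initiation of AZA to the earlier date of the first documentation of relapse, disease progression"; a patient's death also ends it. DCR and DOR end at the same kinds of event. None of these definitions stops at azacitidine discontinuation. Section 8.7.4 adds: "The endpoints of PFS, TTNT, and OS will use FAS". PFS therefore includes patients who stop azacitidine while progression-free.

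Table 8-4 (section 8.3) marks "Requirement for Blood Transfusion (record units and frequency" at baseline and at Visits 1 to n, as a Stage 2 item from unstructured records. The Post-treatment cell is empty. In the same table "Complete Blood Count", marrow blasts, peripheral blasts, the IWG 2006 assessment and "If Progression, Date of Progression" are all marked Post-treatment.

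For a patient who stops for toxicity or by decision (Scenario C), Table 8-2 (section 8.2.1) sets the collection end date at 30 days after discontinuation and adds: "Data relating to date of progression, survival, and next treatment will be collected beyond this date".

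**The concern.** The protocol counts progression and relapse after azacitidine stops but does not schedule the data for one of its own criteria. The rule applied at month 3 on treatment is then wider than the rule applied at month 3 after treatment, and the Kaplan-Meier curve joins the two periods as if they were measured alike.

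A missed or late event can only lengthen the observed interval while the patient stays in follow-up. At stake are PFS in patients who stop before progressing, and DCR and DOR in responders who stop before relapsing. Section 8.7.4 says that the results will be compared with Study 5F9005, so ascertainment that changes at treatment stop would carry into that comparison. A later SAP can set censoring rules, but it cannot recover data that were never abstracted.

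**Working it through.** **Step 1: the tables side by side, for a Scenario C patient after the stop.**

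| Route to progression (Table 8-1) | Post-treatment cell, Table 8-4 | Beyond 30 days, Table 8-2 Scenario C |
|---|---|---|
| Physician wording | Marked (date of progression) | Named |
| Blasts | Marked | Not named |
| Granulocytes, platelets, Hb | Marked | Not named |
| Transfusion dependence | Blank | Not named |

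Two gaps follow. Transfusion dependence has no scheduled post-treatment source in either table. Counts and blasts have one in Table 8-4 but not, read literally, in Table 8-2, and section 8.3 refers the reader to section 8.2.1 for start and end times.

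**Step 2: do other provisions close the gap?** Only in part.
- Physician-documented progression remains a valid route.
- Section 8.8 plans to derive composite outcomes by algorithm, which cannot evaluate a criterion without data.
- Independent adjudication (section 8.9) covers CR, rw-CR, PR and rw-PR, not missed progression.
- Section 8.10 says that marrow biopsies are not routine other than at diagnosis and suspected progression, so blood-based and transfusion criteria matter more.

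**Step 3: illustration of size.** The protocol states no PFS figure to reproduce. The one document input is median OS of about 13 months (section 6.1). Everything else is assumed:
- median PFS with full ascertainment, M: 6 to 10 months;
- share stopping azacitidine event-free, s: 20% to 50%;
- share of post-stop progression visible only through transfusion records, m: 10% to 50%.

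With exponential times:
- PFS hazard h = ln2/M
- progression part p = h − ln2/13
- event-free stopping hazard d = h·s/(1−s)
- observed post-stop hazard h₂ = h − m·p
- observed PFS: S(t) = exp(−(h+d)t) + d·[exp(−h₂t) − exp(−(h+d)t)]/(h+d−h₂)

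| M | s | m | h | p | d | h₂ | Observed median | Shift in median | Shift in 12-month PFS |
|---|---|---|---|---|---|---|---|---|---|
| 10 | 20% | 10% | 0.0693 | 0.0160 | 0.0173 | 0.0677 | 10.02 | +0.02 | +0.1 points |
| 8 | 35% | 25% | 0.0866 | 0.0333 | 0.0467 | 0.0783 | 8.13 | +0.13 | +0.9 points |
| 6 | 50% | 50% | 0.1155 | 0.0622 | 0.1155 | 0.0844 | 6.55 | +0.55 | +4.9 points |

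With m = 0 the shift is 0. It is positive whenever m > 0.

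**Step 4: sensitivity to the death assumption.** Using 13 months as the median for death without progression makes progression only 1 − M/13 of the event hazard: 54%, 38% and 23% for M = 6, 8 and 10. That is probably low, because OS includes deaths after progression.

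An alternative assumption is a median of 9 months to progression and 30 months to death without it. Then h = ln2/9 + ln2/30 = 0.1001, M = 6.92 and progression is 0.0770/0.1001 = 77% of the hazard. Median times to event-free stopping of 9 and 4 months give s = 0.0770/0.1771 = 43% and 0.1733/0.2734 = 63%. With m = 20% at the first and 40% at the second, the same formula gives observed medians of 7.19 (+0.26) and 8.12 (+1.20).

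Both models ignore the 30-day window and treat every transfusion-only progression as never recorded. This leans towards a larger shift.

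**The case against.** The strongest case against has four parts.

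- **Progression need not be lost.** Physician wording of worsening suffices under Table 8-1, and its date is collected after treatment. This stands: what is lost is progression derived from transfusion records alone, so the definition narrows but does not disappear.
- **One blank cell is weak evidence of an intended cut-off.** Table 8-4 is loosely built. For example, it marks the IWG assessment post-treatment but not the response assessment date. Data relating to progression in Table 8-2 could be read to include transfusions. This is fair, but neither table says so, and abstractors will follow the tables.
- **Censoring may be settled in the SAP.** It may, and censoring at the stop or at the last adequate assessment would change or remove the effect. The protocol states no such rule.
- **PFS is secondary and described without a test, and the primary CR rate does not use transfusion data.** This is correct and limits the weight of the point.

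A reader might infer more than the documents support:
- That PFS is certainly overstated. The bias depends on continued follow-up and on some progressions appearing only through transfusions.
- That transfusion is the only component lost. Table 8-2 read literally also drops counts and blasts after 30 days.
- That Hb held up by unrecorded transfusions is a second, separate bias. The same masking occurs on treatment, and the difference is again only the missing transfusion criterion.
- That the median shifts by a month or more. This needs the high stopping and progression shares of Step 4, which no document figure supports.

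**Conclusion.** The inconsistency is real. As written, the protocol continues PFS, DCR and DOR past azacitidine stop but schedules no post-treatment source for transfusion dependence, and Tables 8-2 and 8-4 disagree on counts and blasts. For patients who stop without progression, the direction of bias is upward if follow-up continues and if some progression is visible only through transfusions. Scenario B patients already have their progression event and are not affected for PFS.

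The size cannot be derived from the document. Over the assumed ranges of Step 3 it is probably modest: 0.02 to 0.55 months in median PFS, or 0.1 to 4.9 points at 12 months. Shifts of about a month need roughly half or more of patients stopping event-free, progression making up about three quarters of PFS events, and 40% to 50% of it visible only through transfusions. The point merits correction before Stage 2 abstraction but does not touch the primary endpoint.

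**What to change.** 1. Mark transfusion requirement in the Post-treatment column of Table 8-4.
2. Reconcile Scenario C of Table 8-2 with Table 8-4, so that everything the progression and relapse criteria need (transfusions, blood counts, marrow and peripheral blasts) is collected beyond 30 days until progression or relapse, next MDS treatment, death or 01 January 2021. Adding transfusions alone would leave the conflict over counts and blasts. If PFS is to run past next treatment, the collection limit and the censoring rule should be made to agree.
3. If transfusions cannot be abstracted after treatment, state that this criterion applies only on treatment. Then add a PFS sensitivity analysis that censors progression-free patients at their azacitidine data collection end date, so that one definition holds throughout.

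The cost is a little more abstraction, in charts already reviewed for progression date and next treatment. Section 8.1.4 already foresees finalising the eCRF and modifying the protocol after Stage 1. Care given outside the network will still be missed (section 8.10), so capture will improve but not be complete.

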#### 8.4. Data Sources

The primary data source for this retrospective cohort study will be the patient’s EHR supplemented by a chart review. Patients will be identified from a large, comprehensive RWD database. A chart review will be conducted to extract ancillary data from the EHR. Supplemental vitality status will be obtained from the LADMF.

## 8.5. Study Size

A sample size of approximately 400 patients will provide adequate precision to estimate CR rates. The width of a 2-sided 95% exact CI of CR rate is  $\leq 10\%$  for an observed CR rate in the range of 5% to 25% if sample size is  $> 300$ .

95% CIs for observed CR rate for a given sample size are listed below:

**Table 8-5. Observed CR Rates and 95% CI for Given Number of Responders and Sample Size**

| Observed CR rate | 200 Patients
95% CI | 250 Patients
95% CI | 300 Patients
95% CI | 350 Patients
95% CI | 400 Patients
95% CI |
|------------------|------------------------|------------------------|------------------------|------------------------|------------------------|
| 5%               | (2.4%, 9.0%)           | (2.8%, 8.7%)           | (2.8%, 8.1%)           | (3.1%, 8.0%)           | (3.1%, 7.6%)           |
| 10%              | (6.2%, 15.0%)          | (6.6%, 14.4%)          | (6.8%, 14.0%)          | (7.1%, 13.6%)          | (7.2%, 13.4%)          |
| 15%              | (10.4%, 20.7%)         | (11.0%, 20.3%)         | (11.2%, 19.6%)         | (11.6%, 19.3%)         | (11.6%, 18.9%)         |
| 20%              | (14.7%, 26.2%)         | (15.2%, 25.5%)         | (15.6%, 25.0%)         | (15.9%, 24.6%)         | (16.2%, 24.3%)         |
| 25%              | (19.2%, 31.6%)         | (19.9%, 31.1%)         | (20.2%, 30.3%)         | (20.7%, 30.0%)         | (20.8%, 29.5%)         |

## 8.6. Data Management

Data will be abstracted by structured data query and by chart review of unstructured data into an electronic case report form (eCRF). Data extracted from EHR through an eCRF, will be collected in an EDC system. Data from structured query will be compiled together with EDC data for analysis. The data collected are listed in the Variables section (Section 8.3) using the data collection principles. Review of the patient level data will be performed by trained personnel employed by McKesson.

For Stage 1, the main purpose is to assess data completeness. Therefore, data reconciliation, variable derivation, and data analysis will not be conducted. Instead, McKesson will only report the data completeness (ie, % of patients with data for each variable) for variables that are directly extracted from EHR. In addition, chart abstraction on select variables and outcome parameters will be conducted on approximately 20 patients. In Stage 2, full data abstraction of structured and chart data will be performed, as well as data QC. Study data will be stored on secure McKesson network drives with access restricted to authorized personnel only. Both structured and eCRF data will be transferred to Gilead via Gilead File Transfer Service (GFTS). Personal Health Information, which could identify the patients whose data are being utilized, will not be transferred to Gilead at any time; all data transferred to Gilead will be de-identified.

All data will be stored according to McKesson's retention policy. In accordance with Good Pharmacoepidemiology Practices guidelines, the study archive will be maintained for at least 5 years after final report or first publication of study results, whichever comes later. The data will be maintained on a secure data server with appropriate access restrictions.

